#### *9.1.2 Gastrointestinal upset due to the intervention*

With a change in diet, and especially in large changes in diet, participants could experience constipation, diarrhea, nausea, heartburn, etc. These effects usually subside after several days, but the participant always has access to the study chair, [name], as well as the study registered dietitian to discuss how to relieve these effects. The physician will determine if gastrointestinal symptoms are consistent with initiation of chemotherapy or if they could be due to the diet.

Probability: Moderate

Magnitude: Low to high

Duration: Short-term

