### **4. Study design**

#### *4.1 Brief description and specific aims*

This will be a feasibility pilot randomized controlled trial performed at a single site. We will recruit 42 patients with cancer who are beginning a chemotherapy regimen and randomize them 2:1 to the intervention group or usual care (28 in the intervention arm and 14 in the usual care arm). The uneven allocation serves to improve recruitment, as some patients are disappointed to be assigned to the usual care arm, and allows us to get more information about the intervention. This will be an open label study (due to the nature of the intervention it is not possible to blind participants, and due to the active involvement of the PI in data acquisition, it is not feasible to blind the PI). At baseline, participants will complete an on-study form that includes demographics and clinical characteristics. They will complete a 3-day food record (ideally from two weekdays and one weekend day), a fasted blood draw, and several questionnaires [i.e., 14-Item Mediterranean Diet Assessment Tool, Functional Assessment of Chronic Illness Therapy – Fatigue (FACIT-F), Aerobics Center Longitudinal Study (ACLS) physical activity questionnaire, Brief Fatigue Inventory (BFI), 27-item Symptom Inventory, Functional Assessment of Cancer Therapy-Cognition (FACT-Cog), Brief Pain Inventory (BPI), Insomnia Severity Index (ISI)]. For the duration of the study, all participants will complete a daily diary that includes their average fatigue level that day. For 4 weeks, we will provide participants in the intervention group with food based on the Mediterranean Diet. We intend this food to be substituted or supplemented with other food of the patients' choosing, though we encourage participants to comply with the Mediterranean Diet for all meals and snacks. During this time we will also provide education regarding the principles and composition of the Mediterranean Diet and how to effectively implement it at home. This education will include materials that encourage behavior change to inspire motivation and adherence to the diet. At 4 weeks, participants will undergo a mid-point evaluation where they will complete the same assessments as at baseline except for the on-study form. For weeks 5-8, participants in the intervention group will be encouraged to follow the Mediterranean Diet though we will not provide food. During the 8-week intervention, we will be in contact with participants in both groups to monitor adverse events and discuss any barriers to consuming the diet (in the intervention group). At 8 weeks, participants will repeat the assessments and undergo an exit interview, which will last approximately 15-30 min. Participants will receive \$20 total to complete baseline and post-intervention measures and those in the intervention group will receive free meals for 4 weeks. Those in the usual care group will be offered the intervention materials and one week of meals *gratis* at the conclusion of the study.

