## 9. Risks to subjects

### 9.1 Risks to subjects and adequacy of protection against risk

#### 9.1.1 Weight loss due to the intervention

Some studies have documented weight loss upon adoption of the Mediterranean Diet despite consuming calories *ad libitum*. Our intervention diet will be *ad libitum* and participants will be encouraged to satisfy thirst and hunger. However, due to the satiating nature of the Mediterranean Diet compared to the typical Western diet, and the fact that they are initiating chemotherapy, there is a chance that patients could enter a calorie deficit and lose weight during the course of the intervention. If the patient is overweight or obese, slow weight loss will not be considered an adverse event (less than approximately 3% of their body weight per week). Weight measured from clinical visits will be recorded by study staff and used to assess rapid weight loss. If a patient experiences rapid, unintentional weight loss, as monitored and determined by the treating oncologist, the physician will determine how to intervene. It is important to determine what is causing the weight loss. If it is suspected that the study meals are contributing, the physician could recommend:

- Reviewing food records to see if there are any new foods that the patient is consuming from the intervention diet that they could have an unexpected reaction to; for example, there could be an ingredient to which the participant has an intolerance, leading to nausea and/or diarrhea and contributing to the weight loss,
- Discontinuing consumption of all study-related foods, and/or
- Other relevant actions on the patient-level.

Rapid, unintentional weight loss could be a symptom of another underlying condition, such as the onset of diabetes, cachexia, etc. If it is determined that the study foods are not contributing to the weight loss, the physician will decide if it is safe for the patient to continue with the study. We will follow the Common Terminology Criteria for Adverse Events (CTCAE), version 5, to record weight loss as an adverse event:

- Weight loss 5 – <10% from baseline with no intervention indicated will be considered a Grade 1 adverse event.
- Weight loss of 10 – <20% from baseline and indicated nutritional support will be considered a Grade 2 adverse event.
- Weight loss  $\geq 20\%$  from baseline with indicated tube feeding or total parenteral nutrition will be considered a Grade 3 adverse event.

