## 16. Data analysis and monitoring

### 16.1 Adverse event reporting

An **adverse event** is any symptom, sign, illness, or experience that develops or worsens during the study, whether or not the event is considered related to the intervention. To assess the severity of adverse events, we will use the CTCAE, version 5, recommended by the NCI. The CTCAE displays Grades 1 through 5 with unique clinical descriptions of severity for each adverse event based on this general guideline:

- **Grade 1:** Mild; asymptomatic or mild symptoms; clinical or diagnostic observations only; intervention not indicated.
- **Grade 2:** Moderate; minimal, local or noninvasive intervention indicated; limiting age-appropriate instrumental activities of daily living.
- **Grade 3:** Severe or medically significant but not immediately life-threatening; hospitalization or prolongation of hospitalization indicated; disabling; limiting self-care activities of daily living.
- **Grade 4:** Life-threatening consequences; urgent intervention indicated.
- **Grade 5:** Death related to adverse event.

A **serious adverse event** is any adverse medical experience that results in death, or is life-threatening, or requires inpatient hospitalization of at least 24 hours, or prolongs existing hospitalization, or results in persistent or significant disability/incapacity, or causes a congenital anomaly/birth defect, or requires medical or surgical intervention to prevent permanent impairment or damage.

Each adverse event will be evaluated in regard to whether the adverse event was potentially a consequence of the intervention. Attribution will be categorized into one of five categories (**Table 5**). The subject's referring oncologist, designee, or study medical monitor will determine the grade and attribution.

Attribution	Description
Unrelated	The adverse event is clearly NOT related to the intervention
Unlikely	The adverse event is doubtfully related to study intervention
Possible	The adverse event may be related to study intervention
Probable	The adverse event is likely related to study intervention
Definite	The adverse event is clearly related to study intervention

**Table 5.** An assessment of the relationship between the adverse event and the study intervention will be categorical.

With that information, **we will only report the following events:**

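### Diet-related weight loss and gut symptoms are judged patient by patient while everyone is on chemotherapy, and no by-arm summary of adverse events or weight is planned

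*Combined protocol and SAP*

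**What the plan says.** **Attribution.** For gut symptoms, 9.1.2 says: "The physician will determine if gastrointestinal symptoms are consistent with initiation of chemotherapy or if they could be due to the diet". For weight, 9.1.1 says: "If a patient experiences rapid, unintentional weight loss, as monitored and determined by the treating oncologist, the physician will determine how to intervene". For adverse events in general, 16.1 says: "The subject's referring oncologist, designee, or study medical monitor will determine the grade and attribution", using five categories from unrelated to definite. Section 4.1 states "This will be an open label study", and no blinded attribution is described.

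**Data collected.** Section 4.1 says "we will be in contact with participants in both groups to monitor adverse events", and 14.3 makes this contact roughly weekly. Section 9.1.1 says "Weight measured from clinical visits will be recorded by study staff and used to assess rapid weight loss"; it names no other use for those weights.

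**Expected harm.** Section 9.1.1 gives a high probability of some weight loss and a low probability of a dangerous amount. Section 9.1.2 rates gut upset as moderate.

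**What counts as an event.** For overweight or obese patients, 9.1.1 says "slow weight loss will not be considered an adverse event (less than approximately 3% of their body weight per week"). The same section sets weight-loss grades that start at 5%, 10% and 20% from baseline.

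**Analysis.** Section 17 compares the arms on baseline variables, Mediterranean Diet score, FACIT-F fatigue, biomarkers and other questionnaires. It names no comparison of adverse events, gastrointestinal events or weight. The list in 16.1 introduced by "we will only report the following events" concerns reporting to oversight bodies and is not an analysis.

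**The concern.** Nausea, diarrhoea and weight loss in one patient starting chemotherapy can fit the drugs, the diet or both. No reading of the single case separates them reliably, whoever does it. A comparison with patients who have the same chemotherapy background and no study diet does so on average, and the trial has that group. Section 4.6 uses exactly this reasoning for fatigue: a control arm is needed to show what happens without the intervention. It applies equally to weight and gut symptoms.

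Two things are at stake. First, the results are meant to inform a larger trial (Sections 1 and 17.4.2), which will need an estimate of the excess weight loss and gut events on the diet. Second, Section 2.1.3 hypothesises metabolic benefit without weight loss. If weight change is not shown by arm, the glucose and insulin results cannot be read against that hypothesis.

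**Working it through.** **1. The plan's own figure.** The documents give no power, precision or event rate for weight or adverse events. The only power statement is for FACIT-F in 17.1: n = 33 (22:11), effect size 0.75, correlation 0.50, two-sided 0.15, 80% power.
- Residual SD = sqrt(1 − 0.50²) = 0.866.
- SE = 0.866 × sqrt(1/22 + 1/11) = 0.866 × 0.369 = 0.320.
- Power ≈ Φ(0.75/0.320 − 1.440) = 81.7%, or 80.6% with the noncentral t on 30 df.

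The stated 80% is reproduced, so 22:11 and 28:14 are sound sizes to use below.

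**2. Which data by arm have a planned comparison?**

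| Data | Collected in both arms | By-arm analysis in Section 17 |
|---|---|---|
| FACIT-F fatigue, diet score, biomarkers | Yes | Yes (17.4.1 to 17.4.3) |
| Other questionnaires | Yes | Yes, exploratory (17.4.4) |
| Adverse events, including gut events | Yes (4.1, 14.3) | None |
| Clinic weight | Recorded (9.1.1) | None |

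**3. Precision for mean percent weight change.** The SD is an assumption, with a range of 3 to 5 percentage points. Half-width of the 95% CI = t × SD × sqrt(1/n₁ + 1/n₂).
- 22:11 (t = 2.04 on 31 df): 2.26, 3.01 and 3.77 points for SD 3, 4 and 5.
- 28:14 (t = 2.02 on 40 df): 1.98, 2.65 and 3.31 points.

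**4. Precision for event proportions.** The rates are assumptions: 20% to 50% in controls, with a 20-point excess on the diet. Half-width = 1.96 × sqrt(p₁(1 − p₁)/n₁ + p₂(1 − p₂)/n₂).
- 28:14, 40% against 20%: 1.96 × sqrt(0.24/28 + 0.16/14) = 1.96 × 0.141 = 28 points. Over the range: 28 to 31.
- 22:11, same rates: 1.96 × sqrt(0.24/22 + 0.16/11) = 31 points. Over the range: 31 to 35.
- Power for a 20-point excess at two-sided 0.15 (normal approximation): 41 to 44% with 28:14 and 36 to 38% with 22:11.

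**5. The slow-loss exclusion against the grades in 9.1.1.** At the limit of 3% per week, cumulative loss is 1 − 0.97ʷ after w weeks.
- Week 2: 5.9%. Week 4: 11.5%. Week 8: 21.6%.
- If the 3% is counted on baseline weight instead: 12% at week 4 and 24% at week 8.
- A far slower rate also reaches the first cut-off: 1 − 0.95^(1/8) = 0.64% per week gives 5% by week 8.

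An overweight or obese patient could thus stay under the weekly limit, which 9.1.1 says is not an adverse event, and still pass the percentage cut-off of a grade. Adverse-event counts alone may then understate weight loss. Measured percent change does not depend on how the two passages are reconciled.

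**The case against.** The strongest reply is that patient-level attribution is normal practice and that the plan is less one-sided than it may look. Much of this stands, and it rules out several stronger readings.

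- **That the diet is cleared by default.** A reader might infer this because nearly any symptom fits chemotherapy. But 9.1.2 asks only whether symptoms could be due to the diet, 16.1 has a category for possible relation, and 9.1.1 suggests that weight loss can be read reassuringly as an effect of dietary change. Error could run in either direction.
- **That harm is missed or the control arm never used.** Grade 4 or 5 events go to the review board whatever their attribution (16.1). The safety committee receives the adverse-event spreadsheet and serious events, including unrelated unexpected ones (16.2). The symptom inventory is completed in both arms and probably falls under the by-arm analysis in 17.4.4, although that section does not name it and the text lists no nausea or diarrhoea item. None of this is a by-arm analysis of adverse events or weight.
- **That the attributing physicians are documented as unblinded.** The documents name only participants and the principal investigator. It is a fair inference, since 9.1.1 lets the physician advise stopping study foods, but no more than that.
- **That the weight interval is adequate because it is narrower than 5 points.** The 5% cut-off is for one patient's loss and the interval is for a difference in means. The comparison has no inferential meaning.

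The by-arm comparison has limits too. Randomisation does not protect self-reported symptoms from open-label reporting, and weekly contacts in the diet arm also cover barriers and compliance, which may draw out more complaints. Weight is not among the scheduled assessments in Table 4. Table 3 puts 4-weekly infusions at weeks 1 and 5 only, so a clinic weight near week 8 may be off schedule or absent.

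**Conclusion.** The point holds as a gap in the analysis plan. The cause of weight loss and gut symptoms is settled by individual judgement in an open-label trial with a competing cause in every patient, and no summary by randomised arm is planned. Harm from the diet may be misattributed in either direction and is left unquantified. The documents do not show that it would go undetected.

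The gain is descriptive. Under the assumed SD of 3 to 5, mean percent weight change would be estimated to within about 2 to 4 points. Under the assumed rates, differences in event proportions would be known only to within about 28 to 35 points. The table would not reliably detect a moderate excess of gut events, but it would give the larger trial an estimate that does not rest on attribution. The conflict within 9.1.1 follows from the plan's own figures and needs no assumption about rates.

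**What to change.** Add to 17.4 a descriptive table by randomised arm, regardless of attribution, with 95% CIs and no hypothesis test:
- mean percent weight change from baseline to weeks 4 and 8, using the nearest clinic weight within a stated window, with the number missing per arm;
- the proportion losing 5% or more;
- the proportions with any gastrointestinal event and with a Grade 2 or higher event.

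Ask the same adverse-event questions at the weekly contacts in both arms. Leave physician attribution as it is for patient care and for the reporting in 16.1 and 16.2. Reconcile the slow-loss exclusion in 9.1.1 with the weight-loss grades in the same section.

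The cost is one table and a fixed set of check-in questions, mostly from data already collected. The downsides are wide intervals, clinic weights that may be off schedule, and gut events that remain open to open-label reporting bias. The table must be labelled descriptive.

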#### *9.1.3 Emotional distress due to the intervention or the outcome measures*

There is a chance that participants could become emotionally distressed by the expectation to consume all of the food provided to them. We will reassure each patient regularly that the food is there to enhance adherence to the Mediterranean Diet for our study, but they are not limited to these foods and they do not need to consume them.

Our questionnaires contain information that might be distressing or private (e.g., “I am satisfied with family communication about my illness” from the FACIT-F). We will remind the patients that they do not have to answer any questions they are not comfortable answering, and they can take a break or stop answering the questionnaires at any time.

Probability: Low

Magnitude: Low

Duration: Short-term

#### *9.1.4 Risks from a blood draw*

Bruising, bleeding, and pain could occur where the blood samples are taken. Sometimes, drawing blood causes people to feel lightheaded or even faint. To avoid these risks, all blood will be drawn at the Wilmot Cancer Institute or UR Labs by trained staff. Specifically, to minimize the chance of bruising and the slight chance of infection associated with blood collection, the labs employ standardized hospital procedures for blood collection, and use a trained phlebotomist and sterile materials. Participants will be encouraged to be well hydrated before and after the blood draw, and to consume food soon after the blood draw.

Probability: Low

Magnitude: Low

Duration: Short-term (days at the most)

#### *9.1.5 Breach of confidentiality*

There is always a risk of a breach of confidentiality in which sensitive medical information could become known to persons outside the research team. To avoid leakage of sensitive information, only [name] (the study chair) and any individual designees will have access to the screening log and the file that links subject name with subject number (both will be encrypted); these files will be stored on a

password-protected computer in her private office in the Cancer Control Unit in Saunders Research Building. All data files will reference participants by a non-identifiable Participant ID and will be stored on [name] computer and secure servers at URMC. Paper consent forms will be stored in a locked cabinet also in her office. E-Consent forms will be stored in a URMC Box drive accessible to only [name] and the study coordinator. If [name] shares data with any other researcher for analyses, all data will be deidentified (i.e., void of name, birthdate, and contact information). Presentation of data in the form of posters, presentations, and manuscripts, either in private or public settings, will not have any identifiable information. [name] and all other co-investigators participate in ethical training in accordance with URMC policies (e.g., online coursework via the CITI collaborative).

Probability: Very low

Magnitude: Low to high

Duration: Unknown

#### *9.1.6 Risk to groups or society*

There are no known risks to groups or societies.

#### *9.2 Alternatives to participation*

The patient can seek other nutritional services in addition to or instead of participating in this study. Patients may choose to not participate in the study without penalty or effects on subsequent medical care.

### **10. Potential benefits to participants**

Participants may or may not directly benefit from this study. Participants will be provided with information on the Mediterranean Diet as well as healthy Mediterranean Diet meals for 4 weeks, which they have the option of eating instead of or in addition to food they purchase and prepare on their own. We predict that the diet will have a positive effect on their symptoms, though it may not.

### **11. Costs for participation**

There will be no costs to the participants or the participants' insurance for assessments, screening tests, instruments/equipment, or parking. The participants will be responsible for travel to and from the research site. The participants will be responsible for storing the meals (in the freezer or refrigerator) and heating the prepared meals, if desired.

There might be concern that eating a Mediterranean Diet is more expensive than a participants' previous eating habits. However, the recipes that we are providing cost approximately \$4.50/meal for lunch and dinner. If the participants are avoiding restaurants, red meat, and prepared foods, it is likely that they will spend less. Indeed, when directly assessing food cost based on amount of nutrients purchased, a Mediterranean Diet specifically and a more healthful diet in general is not more expensive than a less healthy diet.

### **12. Payment for participation**

Participants will receive \$20 after they finish the study.

### **13. Participant withdrawals**

Participants may discontinue participation in the study at any time if they do not wish to take part any longer. Participants may be withdrawn from the study by research personnel if it is deemed in their best interest to no longer participate or in the case of lack of cooperation, non-compliance, or other administrative reasons. In the event that a participant does withdraw from the study, the information they have already provided will be kept in a confidential manner. A 10-20% withdraw rate is built into the study design and recruitment goal, so there should not be a need to replace participants who withdraw before completing the study. Participants may opt to not engage any of the assessments (e.g., any given questionnaire, blood draw, etc.), and still complete the rest of the study. For participants who do not complete study, available data will be utilized during the analysis.

### **14. Privacy and confidentiality of participants and research data**

#### *14.1 Steps taken to protect privacy*

##### *14.1.1 Assignment of Participant Identification (ID) number*

The study team will assign a numerical Participant ID to each subject once they have signed the consent form (e.g., 101, 102, etc.). Notes and databases will use this number and the subject's first and last initials as identifiers to ensure data integrity. Other identifying information will not exist on these forms. A complete list of study participants with Participant ID, name, and contact information will be maintained separately for the purpose of contacting subjects if necessary; this database will be maintained for at least six years after the study is complete. This linkage information will be maintained and only accessible to [name], the study chair, who will provide individuals with private access only if necessary. All data files will reference participants by the Participant ID and will be stored on [name] computer and secure servers at URMC.

